8.2.2 Treatment-Emergent Adverse Events by Intensity

Adverse events are categorized for severity by the investigator as "Mild", "Moderate" or "Severe". The frequency of TEAEs by intensity will be summarized by body system, and preferred term, overall and by treatment group. TEAEs with missing intensity will be considered 'Severe' in the tabular summaries but data listings will show severity listed as missing. In case of multiple TEAEs for the same body system and preferred term for the same subject, only the TEAE with the maximum intensity will be counted in the table.

8.2.3 Treatment-Emergent Adverse Events Related to Study Drug

Related AEs are the AEs with "Related" or "Possibly Related" for causality. TEAEs with missing relationship to study drug will be considered "related" in the tabular summaries but data listings will show relationship as missing.

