9.6 Assessment of Causality

The Investigator's assessment of the relationship to study drug of an AE is part of the documentation process but is not a factor in determining whether or not it is reported. All AEs, regardless of causality, must be reported. The blind should not be broken for the purpose of making this assessment. If there is uncertainty as to whether a clinical observation is an AE, the event should be reported.

The relationship of the event to the study drug should be determined by the Investigator according to the following criteria:

Not related An event for which sufficient data exist to indicate that the etiology is unrelated to the drug.

Amendment 5: 28 Mar 2016

Unlikely related An event that does not follow a reasonable temporal sequence relative to administration

of the drug. However, causality from the drug cannot be ruled out.

Possibly related An event that follows a reasonable temporal sequence relative to administration of the

drug; that follows a known or expected pattern of response to the drug; but that could

readily have been produced by other factors.

Probably related An event that follows a reasonable temporal sequence relative to administration of the

drug; that follows a known or expected pattern of response to the suspected drug; and that could not be reasonably explained by the known characteristics of that patient's

clinical state.

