11.5 Safety Analysis

All AEs will be coded using MedDRA. The number and percentages of patients reporting at least one occurrence of each AE will be tabulated by system organ class and preferred term. The number and percentages of patients reporting at least one occurrence of each AE by system organ class and preferred term will also be tabulated by severity and by the relationship to study drug. For multiple occurrences of the same AE in a patient that differ in severity, the AE with the highest level of severity will be tabulated. For multiple occurrences of the same AE in a patient that differ in relationship to study drug (e.g., related and not related), the AE will be tabulated as related. All AEs for all patients will be presented in a data listing.

All other safety parameters will be summarized using descriptive statistics and presented by time point and treatment group. All other safety parameters will be presented for individual patients in data listings.

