8.2.1 Treatment-Emergent Adverse Events

A treatment-emergent adverse event (TEAE) is defined as any AE started post-treatment. Summary tables will include number of subjects with treatment-emergent AEs and as percentage of number of subjects in the treatment group. The number of serious TEAEs will be summarized in the appropriate summary table. Summary tables will also be presented for the frequency of AEs by MedDRA-preferred term and severity of AE. Severity of AEs will be based on the scale as indicated in Section 8.2.2.

The subset of AEs that are considered by the Investigator to have a possible or definite relationship to study medication will be considered as treatment-related AEs. If the Investigator does not specify the relationship of the AE to study medication, the AE will be considered as treatment-related. The incidence of AEs and TEAEs will be tabulated per treatment. AEs will also be summarized by severity, using the categories described in Section 8.2.2.

26

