	Treatment Visit for HAQ-DI – ITT population
14.2.2.8	ANCOVA Analysis of The Mean Change from Baseline to the End-of-
	Treatment Visit for HAQ-DI – PP population
14.2.3.1	Summary of ACR Core Set by Time Point and Treatment Group – ITT
	population
14.2.3.2	Summary of ACR Core Set by Time Point and Treatment Group – PP population
14.2.3.3	Analysis of Secondary Endpoint: The Percentages of Subjects Achieving
	ACR20, ACR50, or ACR70 Responses-ITT population
14.2.3.4	Analysis of Secondary Endpoint: The Percentages of Subjects Achieving
	ACR20, ACR50, or ACR70 Responses – PP population
14.2.3.5a	Bar Chart of ACR20 by SAN300 Treatment Regimen – ITT population
14.2.3.5b	Bar Chart of ACR50 by SAN300 Treatment Regimen – ITT population
14.2.3.5c	Bar Chart of ACR70 by SAN300 Treatment Regimen – ITT population
14.2.3.6a	Bar Chart of ACR20 by SAN300 Treatment Regimen – PP population
14.2.3.6b	Bar Chart of ACR50 by SAN300 Treatment Regimen – PP population
14.2.3.6c	Bar Chart of ACR70 by SAN300 Treatment Regimen – PP population
14.2.3.7	Comparison Analysis for ACR20, ACR50, or ACR70 Responses for Pooled
	Treatment Group Against Placebo – ITT population
14.2.3.8	Comparison Analysis for ACR20, ACR50, or ACR70 Responses for Pooled

Number	Title
	Treatment Group Against Placebo – PP population
14.2.3.9	The logistic regression analysis of percentages of subjects achieving ACR20, ACR50, or ACR70 responses – ITT population
	Tierco, of Tierco responses 111 population
14.2.3.10	The logistic regression analysis of percentages of subjects achieving ACR20, ACR50, or ACR70 responses – PP population
14.2.4.1	Summary of MRI Data by Time Point and Treatment Group – ITT population
14.2.4.2	Summary of MRI Data by Time Point and Treatment Group – PP population
	Safety Analysis
14.3.1.1	Summary of All Adverse Events by Treatment Group- Safety Population
14.3.1.2	Summary of Treatment-Emergent Adverse Events by System Organ Class,
	Preferred Term and Treatment Group – Safety Population
14.3.1.3	Summary of Treatment-Emergent Serious Adverse Events by System Organ
	Class, Preferred Term and Treatment Group – Safety Population
14.3.1.4	Summary of Treatment-Emergent Adverse Events Leading to Study
	Discontinuation by System Organ Class, Preferred Term and Treatment Group – Safety Population
14.3.1.5	Summary of Treatment-Emergent Serious Adverse Events Leading to Study
	Discontinuation by System Organ Class, Preferred Term and Treatment Group – Safety Population

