14.3.1.6	Summary of Treatment-Emergent Adverse Events by System Organ Class,
	Preferred Term, Maximum Intensity and Treatment Group – Safety Population
14.3.1.7	Summary of Treatment-Emergent Adverse Events related to Study Drug, System

Number	Title
	Organ Class, Preferred Term and Treatment Group – Safety Population
14.3.1.8	Listing of Deaths – Safety Population
14.3.2.1	Summary of Mean and Mean Change from Baseline in Hematology/Coagulation Results by Treatment Group – Safety Population
14.3.2.2	Summary of Mean and Mean Change from Baseline in Blood Chemistry Results by Treatment Group – Safety Population
14.3.2.3	Summary of Mean and Mean Change from Baseline in Urinalysis Results (pH and Specific Gravity) by Treatment Group – Safety Population
14.3.2.4	Summary of Urinalysis Results (Other Parameters) by Treatment Group – Safety Population
14.3.2.5	Summary of Shift from Baseline in Hematology/Coagulation Results by Treatment Group – Safety Population
14.3.2.6	Summary of Shift from Baseline in Chemistry Results by Treatment Group – Safety Population
14.3.2.7	Summary of Shift from Baseline in Urinalysis Results by Treatment Group – Safety Population
14.3.2.8	Summary of Post-Baseline CTC Grades Increase – Safety Population
14.3.2.9	Summary of Study Specific Laboratory Test Results by Treatment Group – Safety Population
14.3.3	Summary of Mean and Mean Change from Baseline in Vital Signs by Treatment Group – Safety Population
14.3.4	Summary of ECG parameters by Treatment Group – Safety Population

Listings

Number	Title
16.2.1	Subject Disposition – All Randomized Subjects
16.2.2	Analysis Population – All Randomized Subjects
16.2.3.1	Protocol Deviations – All Randomized Subjects
16.2.3.2	Inclusion and Exclusion Criteria – All Randomized Subjects
16.2.4.1	Demographic Characteristics and Informed Consent – All Randomized Subjects
16.2.4.2	Medical History – All Randomized Subjects
16.2.5.1	Drug Exposure Information – All Randomized Subjects
16.2.5.2	Methotrexate Initial Dosage - All Randomized Subjects
16.2.5.3.1	Prior and Concomitant Medications – All Randomized Subjects
16.2.5.3.2	Prior RA Treatments – All Randomized Subjects
16.2.5.3.3	History of Biologics – All Randomized Subjects
16.2.6.1	Disease Activity Score with 28-joint count using CRP (DAS28-CRP) Results – All Randomized Subjects
16.2.6.2	ACR Core Set Measurements Results – All Randomized Subjects

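### The SAP's two definitions of a drug-related adverse event both leave out 'Probably related', the strongest causality level in the protocol

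*SAP*

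**What the plan says.** Protocol 9.6 (Assessment of Causality) instructs the investigator to grade each event on a four-level scale: *Not related*, *Unlikely related*, *Possibly related* and *Probably related*. The last is the strongest: "Probably related An event that follows a reasonable temporal sequence relative to administration of the" drug, with a known or expected response pattern and no reasonable explanation in the patient's clinical state. There is no level called 'Related' or 'Definite'. For *Unlikely related*, the protocol adds: "However, causality from the drug cannot be ruled out".

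The SAP reduces causality to related or not related in two places, in different words:

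- SAP 8.2.1: AEs that the investigator judges "to have a possible or definite relationship to study medication will be considered as treatment-related AEs".
- SAP 8.2.3: "Related AEs are the AEs with 'Related' or 'Possibly Related' for causality".

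Both sections count a missing relationship as related in the tables. SAP 8.2.3 adds the qualification "but data listings will show relationship as missing".

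Protocol 11.5 asks for AEs to be tabulated by relationship. It gives a repeat-event rule for the same AE in one patient: for occurrences "that differ in relationship to study drug (e.g., related and not related), the AE will be tabulated as related". It does not say which of the four levels fall on which side.

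The display that depends directly on the definition is Table 14.3.1.7 in SAP Appendix 2, whose title begins "Summary of Treatment-Emergent Adverse Events related to Study Drug, System".

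**The concern.** A definition of a related event has to be written in the labels that the data carry. These two are not written in the protocol's labels, they do not agree with each other in wording, and no text links them to the scale in protocol 9.6. The level left unnamed is the one that matters most in a related-event table. A program that matches the SAP's labels against protocol-scale data would keep a weaker level and missing values and drop the strongest level. That runs against the cautious approach the SAP itself takes by counting missing causality as related.

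Safety and tolerability is the primary objective, and the groups are very small, so the related-event table will be read closely and one patient changes a percentage visibly.

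**Working it through.** The check is a comparison of labels, followed by the weight of one patient. The plan states no figure on this point to reproduce.

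**Step 1. Match the labels.**

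| Level in protocol 9.6 | SAP 8.2.1 (possible, definite) | SAP 8.2.3 ('Related', 'Possibly Related') | Literal result in Table 14.3.1.7 |
|---|---|---|---|
| Not related | not named | not named | left out |
| Unlikely related | not named | not named | left out |
| Possibly related | matches 'possible' | matches 'Possibly Related' | counted |
| Probably related | not named | not named | **left out** |
| Missing | counted as related | counted as related | counted |

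Each SAP definition matches one of the four protocol levels. Each also contains one label that matches none: 'definite' in 8.2.1 and 'Related' in 8.2.3. 'Probably related' is named in 0 of the 2 definitions.

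**Step 2. Which outputs are exposed.** Table 14.3.1.7 is exposed directly. SAP 8.2.1 defines treatment-related AEs in general terms, so another display could use the same flag. Table 14.3.1.1, titled "Summary of All Adverse Events by Treatment Group- Safety Population", is a candidate, but its contents are not specified and this cannot be settled. Not exposed are the all-causality TEAE endpoint in SAP 2.2.2 and Listing 16.2.7.1, which holds every event.

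**Step 3. Weight of one affected patient.** The documents give no causality counts, so the total effect cannot be calculated. What can be calculated is the drop in the reported related-TEAE rate for each patient whose only related event is graded 'Probably related', which is 1/n:

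- SAN-300 group, n = 6 (Protocol 3.2.2 and 5.1): 1/6 = 16.7 percentage points.
- Pooled placebo, n = 10 (Protocol 3.2.2 and 11.1; 5 cohorts × 2 = 10): 1/10 = 10.0 points.
- Pooled placebo, n = 12 (six cohorts in the dose table; 6 × 2 = 12): 1/12 = 8.3 points.

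The placebo range is kept because the protocol gives 10 pooled placebo patients while describing six cohorts of two, and the actual count is not stated. The SAP leans towards 10: it calls Cohort F optional, SAP 7.1 lists five SAN-300 groups, and SAP 3.5 reports 41 randomized, closer to 5 × 8 = 40 than to 6 × 8 = 48.

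The lower bound is 0, if the eCRF stores the top level as 'Related' or the program treats 'Probably related' as related.

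**The case against.** The strongest reply is that the harm depends on a document not available here. If the eCRF offered 'Related' and 'Possibly Related', SAP 8.2.3 would work as written. That is plausible: the SAP puts those labels in quotation marks, and it was written when 41 subjects had already been randomized. This stands as a limit on the size of the effect. It does not remove the need for a mapping, because the eCRF would then depart from protocol 9.6, and the SAP should say so.

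A second reply is that the two SAP sections can be read as one rule, with 'definite' in 8.2.1 meaning 'Related' in 8.2.3, and that a sensible programmer would place 'Probably related' under 'Related'. Both readings are reasonable, and the authors very probably meant to include the top level. But the text does not say so, and a pre-specified definition should not depend on the programmer correcting it. The more substantive gap is between the SAP and the protocol, rather than between the two SAP sections.

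Third, Protocol 11.5 calls for tabulation by relationship, and a table by recorded level would show these events. SAP Appendix 2 lists no such table, only the related-event summary, so this helps only in part.

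Fourth, the consequence is confined to descriptive output. Dose escalation rests on blinded review of AEs, laboratory results, vital signs and withdrawals, and neither that review nor the stopping rules use Table 14.3.1.7. The listings keep every event, and SAP 8.2.3 implies that they show the recorded relationship, so a careful reader could find an omission. All of that is correct. It bounds the damage but does not make the summary table right.

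**Conclusion.** The concern holds and should be fixed. The label mismatch is certain from the text. The loss of events from the table is conditional: it happens only if causality was recorded on the protocol 9.6 scale and the SAP wording is programmed literally.

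Under those two assumptions, and with the planned group sizes, the one-patient weights in the working apply. They are not a forecast of how often such patients occur. No efficacy result or all-causality safety summary is affected.

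**What to change.** Put one definition in SAP 8.2.1 and 8.2.3, written in the protocol 9.6 labels:

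- Related: *Possibly related*, *Probably related*, or missing.
- Not related: *Not related* or *Unlikely related*.

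State the grouping of *Unlikely related* openly. Placing it under not related keeps what the SAP already does by omission, but protocol 9.6 does not group that level and says a causal role remains open, so the choice should be visible. If the eCRF labels differ from protocol 9.6, add the mapping from each eCRF label to the protocol level.

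Apply the same definition to every related-AE display and to the repeat-event rule in Protocol 11.5. Restating that rule in the SAP is optional.

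The cost is a short text change in two SAP sections and one format in the AE program. No new data are needed. The reported related-TEAE rate may be higher than under the literal reading.

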8.2.4 Treatment-Emergent Serious Adverse Events

Any AE reported as serious in the Case Report Form (CRF) will be reported as a serious adverse event (SAE). The clinical database will be reconciled with the SAE database (from the Salix Safety department) before database lock.

All treatment-emergent SAEs will be summarized by body system and preferred term, overall and by treatment group.

8.2.5 Treatment-Emergent AEs that Led to Premature Discontinuation of Study

All TEAEs that led to subject discontinuation from the study will be summarized and listed separately.

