3.4.1 Stopping Rules for Individual Patient Dosing

The dosing of an individual patient will be stopped under the following circumstances:

- The patient experiences a confirmed reduction in ANC to < 1.0 × 10³/μL.
- The patient experiences a clinically significant atypical or opportunistic infection (including those listed in Appendix 1).
- The patient experiences a clinically significant adverse event related to study participation, in the opinion of the investigator or Sponsor.

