3.5 Study Safety Committee

The Study Safety Committee will be composed of, at a minimum, a Sponsor representative and two independent expert physicians. This committee will review ongoing blinded study safety data, decide whether dose escalation is appropriate (see Section 3.1 for the role of safety reviews in dose escalation), recommend any modifications in dosing, and evaluate whether resumption of individual patient dosing or study enrollment is permissible after any interruption triggered by the stopping rules for patient dosing and for study enrollment (see Section 3.4).

Santarus, Inc.
SAN-300 Clinical Trial Protocol: C2013-0302

Amendment 5: 28 Mar 2016

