5 SUBJECT DISPOSITION

Subject disposition will be summarized for all randomized subjects and will include the number of subjects randomized; number and percentage of subjects who completed or prematurely discontinued the study, classified by reasons for premature discontinuation; the number of subjects randomized at each study site; and the number and percentage of subjects who completed or discontinued the study at each study site.

The number and percentages of subjects in each population and reason for exclusion from population will be summarized for all randomized subjects.

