8.2.6 Treatment-Emergent SAEs that Led to Premature Discontinuation of Study

All treatment-emergent SAEs that led to subject discontinuation from the study will be summarized and listed separately.

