16.2.6.3	The Health Assessment Questionnaire – Disability Index (HAQ-DI) Results – All Randomized Subjects
16.2.6.4	Magnetic Resonance Imaging (MRI) Results – All Randomized Subjects
16.2.7.1	All Adverse Events – All Randomized Subjects

Number	Title
16.2.7.2	Serious Adverse Events – All Randomized Subjects
16.2.7.3	Adverse Events Leading to Withdrawal from the Study – All Randomized Subjects
16.2.8.1.1	Hematology Results – All Randomized Subjects
16.2.8.1.2	Hematology Results with CTCAE Grade >= 1 – All Randomized Subjects
16.2.8.2.1	Chemistry Results – All Randomized Subjects – All Randomized Subjects
16.2.8.2.2	Chemistry Results with CTCAE Grade >= 1 – All Randomized Subjects
16.2.8.3.1	Urinalysis Results – All Randomized Subjects
16.2.8.4	Pregnancy Test Results – All Randomized Subjects
16.2.8.5	Hepatitis Panel Results – All Randomized Subjects
16.2.8.6	Laboratory Results with CTCAE Grade >= 3 or Shift >= 2 – All Randomized Subjects
16.2.8.7	Study Specific Laboratory Test Results – All Randomized Subjects
16.2.9.1	Vital Signs – All Randomized Subjects
16.2.9.2	Physical Exam – All Randomized Subjects
16.2.9.3	ECG Results – All Randomized Subjects
16.2.9.4	Abnormal ECG Measurement – All Randomized Subjects

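### The SAP's discontinuation outputs count only AEs that led to leaving the study, so an AE that stops a patient's dosing while the patient stays in follow-up is absent from them

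*SAP*

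**What the plan says.** On the protocol side, Section 3.4.1 opens with "The dosing of an individual patient will be stopped under the following circumstances" and lists three triggers: a confirmed neutrophil count below 1.0 × 10³/µL, an important opportunistic or atypical infection, and an important AE related to participation. It does not say that the patient leaves the study. Section 3.5 asks the Study Safety Committee to "evaluate whether resumption of individual patient dosing or study enrollment is permissible after any interruption triggered by the stopping rules for patient dosing". Withdrawal is handled separately in Section 7.1, where an intolerable AE is one of several example reasons and the 3.4.1 triggers are not named.

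On the SAP side, everything is tied to study status. SAP 5 reports the "number and percentage of subjects who completed or prematurely discontinued the study, classified by reasons for premature discontinuation". SAP 8.2.5 says "All TEAEs that led to subject discontinuation from the study will be summarized and listed separately", and SAP 8.2.6 does the same for serious events: "All treatment-emergent SAEs that led to subject discontinuation from the study will be summarized and listed separately". In SAP Appendix 2, Tables 14.3.1.4 and 14.3.1.5 are titled for study discontinuation, and Listing 16.2.7.3 is titled "Adverse Events Leading to Withdrawal from the Study". No planned output is defined by discontinuation or interruption of study drug, and there is no treatment disposition.

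**The concern.** Safety and tolerability are the primary objective. In a multiple ascending dose trial, readers will look to the AE discontinuation tables for how many patients at each dose could not continue the injections. As planned, those tables answer a different question: how many left the study. The two answers agree only if every patient whose dosing is stopped is also withdrawn, and neither document requires that.

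The same AE, with the same consequence for dosing, could thus be counted at a site that withdraws the patient and not counted at a site that keeps the patient in follow-up. The results are meant to inform the design of later studies, so the tables should not depend on that choice.

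**Working it through.** The plan states no figure to reproduce. It has no sample size calculation and no assumed event rate. The check is a reading of the rules, followed by small arithmetic for scale.

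**Step 1. Are stopping dosing and leaving the study distinct?** Yes.
- Protocol 3.4.1 stops dosing and is silent on participation.
- Protocol 3.5 foresees dosing resuming, which presupposes that the patient is still in the study.
- Where the protocol means removal it says so. Section 5.4 takes a patient off the study after the investigator breaks the blind.
- The early termination visit in Section 10.2.7 is triggered by ending participation, not by ending injections.

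**Step 2. Follow one patient through the outputs.** Suppose dosing stops for an AE after the Day 15 injection and the patient attends through Day 71.

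| Output | What it shows |
|---|---|
| SAP 5 disposition | Not discontinued; probably completed |
| SAP 8.2.5 and 8.2.6, Tables 14.3.1.4 and 14.3.1.5, Listing 16.2.7.3 | Absent |
| Tables 14.3.1.1, 14.3.1.2, 14.3.1.6 and 14.3.1.7 (14.3.1.3 if serious), Listing 16.2.7.1 | AE present where it meets the table's criterion; no link to the dosing stop |
| Exposure (SAP 8.1, Table 14.1.5, Listing 16.2.5.1) | Shortened; no stated link to an AE |

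For a neutrophil trigger there is a further wrinkle. Protocol 9.2 makes a laboratory abnormality an AE only if the investigator judges it clinically significant. Such a stop could therefore appear only in the laboratory outputs (for example Table 14.3.2.8 and Listing 16.2.8.1.2).

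**Step 3. What can exposure reveal?** SAP 8.1 gives duration = last dose day − first dose day + 1. With injections on Days 1, 8, 15, 22, 29 and 36:
- A permanent stop after 1, 2, 3, 4 or 5 injections gives 1, 8, 15, 22 or 29 days.
- All six injections give 36 − 1 + 1 = 36 days.
- A stop followed by resumption through Day 36 also gives 36 days, so the duration summary does not show it.

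**Step 4. Size.** Protocol 11.1 gives 6 SAN-300 patients per cohort and 10 pooled placebo patients.
- One stopped patient who is not withdrawn: 0/6 = 0% (exact 95% CI 0% to 45.9%).
- The same patient counted: 1/6 = 16.7% (exact 95% CI 0.4% to 64.1%).
- In pooled placebo: 0/10 = 0% against 1/10 = 10%.

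**Step 5. How often might it arise?** The documents give no rate, so this is an assumption. If the true chance of a dosing stop is p, the chance of at least one in an arm of 6 is 1 − (1 − p)⁶. That is 26.5% for p = 5%, 46.9% for p = 10% and 73.8% for p = 20%. These figures cover any dosing stop; only patients who then stay in the study are missed.

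**The case against.** The strongest reply has four parts.

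1. *The AE is not lost.* This is correct. A reader might infer that an AE which stops dosing drops out of the safety reporting altogether. The documents do not support that, as Step 2 shows. With 41 patients randomized (SAP 3.5), a determined reader could cross-check the AE and dosing listings by subject. What is missing is the planned link between event and dosing stop, and a count by arm.

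2. *The patient may not be counted as a completer.* This is fair. A reader might take that classification as certain, but neither document defines completion. SAP 9.1 speaks of subjects who discontinue early, before treatment ends, so the SAP may regard stopping treatment as discontinuation. Against this, SAP 5 splits patients by study status only, and someone who reaches the Day 71 Exit Visit fits the completed category best. Probable is the right word.

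3. *The scenario is permitted, not prescribed.* This is also fair. No section says that a stopped patient must remain in follow-up, and Section 7.1 allows withdrawal for an intolerable AE. Some stopped patients will be captured. But that leaves the count dependent on an unspecified decision, which is the point.

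4. *AE discontinuation is not among the safety endpoints in SAP 2.2.2.* True, and those endpoints are unaffected. The SAP nevertheless plans these tables, and they should mean what readers will take them to mean.

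A reader might also infer that the Study Safety Committee would not learn of dosing stops. Protocol 3.4 requires immediate notification of these events and 3.5 gives the committee the decision on resumption, so the gap lies in final reporting.

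**Conclusion.** The point stands as a gap in the discontinuation outputs. Followed as written, the SAP can report 0/6 AE discontinuations in an arm where an individual stopping rule fired, when the count of patients whose dosing was stopped for an AE is 1/6 (16.7%). The exposure summary does not repair this: it gives no reason for a permanent stop and misses a stop with resumption through Day 36.

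The conclusion rests on two conditions: that at least one patient is stopped under 3.4.1 without being withdrawn, which the protocol allows, and that arms have the planned 6 SAN-300 patients. No hypothesis test or listed safety endpoint changes. The change is worth making because tolerability is part of the primary objective, the arms are small and the correction is cheap.

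**What to change.** - **SAP 5:** report study-drug disposition (completed or permanently discontinued, with reason) separately from study disposition, and define completion for each.
- **SAP 8.2.5 and 8.2.6, Tables 14.3.1.4 and 14.3.1.5, Listing 16.2.7.3:** extend to TEAEs leading to discontinuation of study drug, withdrawal from the study, or both, with the two shown separately.
- **Flag** events that met a Protocol 3.4.1 stopping rule, including laboratory triggers not recorded as AEs, and any resumption of dosing.

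The cost is SAP wording and a few extra table columns. A reader might suppose that nothing more is needed because dosing dates and AEs are already captured. The documents do not show that the CRF records the action taken with study drug, and dates alone cannot establish that an AE caused a stop. If there is no such field, add a blinded medical review of dosing and AE records before database lock to attribute the stops. No clinical rule changes.
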